4 STUDY DESIGN

- This will be a prospective, observational 3.5-year cohort study of patients who are undergoing different types of orthodontic AOB treatment followed by retainers.
- The study population will consist of adult patients who are in active treatment for AOB, and expect to have treatment completed within 24 months of enrollment into the study. Approximately 210 orthodontists or dentists who routinely perform orthodontic treatment (approximately 35 in each of the six National Dental PBRN regions) will participate. Actual enrollment will be based on interest and enrollment into the Network, and likely will vary per region. Each practitioner will be requested to enroll approximately 3 - 8 adult patients in active AOB treatment over an approximate 11 -months enrollment period, with an enrollment goal of approximately 840 adult patients across the National Network. No practitioner will contribute more than 15 patients.
- Retrospective data will be collected to explore patient, practitioner, and dentofacial characteristics that influence the treatment recommendations and the accepted treatment plans for patients with AOB.
- The prospective cohort design will allow the investigation of how patient, practitioner, and dentofacial characteristics affect the success of treatment. The treatment provided to the patients will not be influenced at all by participation in the study.
- In addition, this study will allow the assessment of how treatment modalities, retainer regimens, and patient characteristics are associated with treatment stability and patient satisfaction one year after treatment.
- At each routinely scheduled retainer check visit, the patient will be asked to report on their retainer usage, and the practitioner will also be asked to judge retainer use.
- Patients will be asked again about satisfaction with their retainer regimen, as well as esthetics and function, at one year after treatment.
- Patients will participate in the study for approximately 3 years, on average, the duration of the treatment and follow-up phases. Practitioners' participation in the study will be approximately 3.5 years.

5 STUDY ENROLLMENT AND WITHDRAWAL

5.1 Inclusion Criteria

Practitioner:

In order to be eligible to participate in this study, a practitioner must meet all of the following criteria:

- Is enrolled in the National Dental PBRN as a practitioner who is licensed in the United States (US), and does treat patients in the US on a recurring basis.
- Is a “full” participation level member, or willing to change from “information only” or “limited” to “full”.
- Is trained and certified in Human Subjects Protection Training.
- Is willing to complete study-specific training.
- Has attended or viewed a National Dental PBRN orientation session or has attended at least one annual regional meeting of practitioners.
- Is an orthodontist or a dentist that routinely performs orthodontic treatment.
- Has a sufficiently large patient population such that the practitioner estimates he/she can recruit approximately 3 - 8 adult patients in active treatment for AOB, and expect to have treatment completed within 24 months of enrollment into the study.
- Routinely takes cephalometric x-rays before and after treatment.
- Has the ability to upload (via internet) de-identified cephalometric x-ray and digital intra-oral frontal photographs to a central repository.
- Affirms that the practice can devote sufficient time in patient scheduling to allow focused recording of all data required for the study.
- Does not anticipate retiring, selling the practice, or moving during the study.

Patient:

The patient population will come from the National Dental PBRN practices participating in this study.

In order to be eligible to participate in this study, a patient must meet all of the following criteria:

- Must be at least 18 years of age.
- Must have AOB that is defined as one or more incisors that do not have vertical overlap with teeth in the opposing arch. The remaining incisors may have minimal incisor overlap, but none of them can contact teeth in the opposing arch.
This will be determined by examining the patient’s initial cephalometric x-ray, intra-oral photographs, and/or initial plaster or digital casts.
- Must be in active treatment for AOB, and expect to have treatment completed within 24 months of enrollment into the study.

- Must have an initial cephalometric x-ray (taken prior to the beginning of treatment). A cephalometric x-ray created from a cone-beam CT scan is acceptable.
- Willing to comply with all study procedures and be available for the approximate 3-year duration of the study.
- Allow the use of his/her x-rays and photographs that are obtained as part of normal treatment (i.e. before treatment began and at the time of appliance removal) for this research.
- Agrees to receive text messages, emails, and/or phone calls related to the study visits from the practice per the practice's routine contact method.
- Willing to be contacted as needed by each of these entities: the practice, Regional Coordinator (RC), and the Westat CC (the patient's preferred method of contact will be ascertained).
- Willing to provide contact information for at least one other person who will know the patient's whereabouts in the event the patient cannot be reached.

5.2 Exclusion Criteria

Practitioner: No adult AOB patients in active treatment.

Patient: An individual who meets any of the following criteria will be excluded from participation in this study:

- Adults with clefts, craniofacial conditions or syndromes.
- Patients who have significant physical, mental, or medical conditions that would affect their treatment compliance, cooperation, or outcome.
- Patients expecting to move before the completion of the study.
- Patients with initial treatment plans estimated at more than 36 months.

5.3 Strategies for Recruitment and Retention

5.3.1 Practitioner Recruitment and Retention

All National Dental PBRN orthodontists/dentist practitioners at full participation level, or willing to change to full participation level, will be approached for participation in the study. The study team will rely on the RC from the six Regional Administrative Sites (RAS) to help recruit current practitioner participants into the study. Additionally, practitioners will be recruited into the National Dental PBRN with the assistance from the American Association of Orthodontists (AAO). E-mails will be sent to AAO members to inform them of the study and to invite them to enroll in the National Network. Also, the AAO will make efforts to recruit orthodontists at their national and regional meetings.

Practitioners or their institution will be compensated for the time required to do the research, receiving \$100 for each patient he/she enrolls and completes the data collection process for each of the three visits (\$100 for Baseline/Enrollment, \$100 for

End of Active Treatment, and \$100 for Final Study Visit). The RAS will maintain a list of patients for each practitioner, along with key data regarding expected date of appliance removal and subsequent follow-up visit and can assist the offices in tracking the patients throughout the course of the study. Participating practitioners will also receive reminders regarding the expected completion dates for their patients, as well as their dates of recall.

Several other strategies will be employed to reduce practitioner burden. Special attention will be paid to making study procedures as simple and efficient as possible. Study procedures will be performed at enrollment, end of treatment, and at the one year post appliance removal. Additionally, several very short questionnaires will be completed during the retention phase. Many parts of the study forms can be completed outside of patient time, using notes from patient charts or records.

5.3.2 Patient Recruitment

To meet the patient recruitment goals of the study, the National Dental PBRN practitioner will create a list of all their adult AOB patients who are currently in active treatment, and expect to have treatment completed within 24 months of enrollment into the study. Once the list has been created, the practitioner or his/her staff will invite all patients to participate at their routine orthodontic visits. Offices may also elect to invite patients via phone calls. If a practitioner has more than 15 patients on this list, he/she should sequentially select the patients based upon their treatment start dates, beginning with the patient who started treatment the earliest. If some patients decline or withdraw, practitioners can move sequentially down the list to enroll up to 15 patients.

5.3.3 Patient Retention

Patient retention is vital to this study, and Appendix D provides a Patient Retention Plan for maximizing patient participation throughout the duration of the study.

Patients will receive a total \$100.00 in patient incentives for participating in the study. He/she will receive \$25 for the enrollment visit, \$25 for the study visit when his/her braces are removed, and \$50 for the study visit approximately one year after his/her braces are removed.

5.4 Patient Withdrawal

5.4.1 Reasons for Withdrawal

Patients are free to withdraw from participation in the study at any time upon request.

An investigator may terminate a study patient's participation in the study if:

- Any clinical adverse event (AE), laboratory abnormality, or other medical condition or situation occurs such that continued participation in the study would not be in the best interest of the patient.
- The patient meets an exclusion criterion (either newly developed or not previously recognized) that precludes further study participation.

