5.4.2 Handling of Withdrawals

In the case of patient withdrawal from the study, staff will only attempt continued follow-up data collection for patients who are withdrawn due to an unanticipated problem or other safety concerns. In these circumstances, only data related to the completion of reporting requirements for the unanticipated problem will be recorded. For patients withdrawn from the study for any other reason, the date and reason for withdrawal will be recorded, and no additional study data will be collected. Patients withdrawn from the study may continue to receive usual dental care as patients of the participating practitioner; however, additional study data will not be collected (except as noted above).

Replacement of patients who withdraw or discontinue early will be allowed, but only during the initial 11 months patient enrollment period. The practitioner may attempt to enroll one replacement patient for each patient enrolled who withdraws or discontinues during the practitioner-specific enrollment period. No practitioner will contribute more than 15 active patients in total to the analyses.

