6.5 Withdrawal Visit

- Record date and reason for withdrawal.
- If withdrawal occurs during an in-office visit, and if the consent was not withdrawn, obtain the applicable study data using the visit specific data collection forms/steps listed in the sections above.

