- 2) The operational impact of all of the above scenarios can be summarized by two scenarios:
 - a. Patient has a new practitioner (not a National Dental PBRN member)
 - b. Patient stops seeing any practitioner
- 3) Locating the patient should not be a problem (see Methods to Minimize “Lost”), and having the patient agree to continue participating should not be a problem (see Methods to Minimize “Refused”).
- 4) The main operational issue is: How to get study follow-up visit information from patients seeing a non-National Dental PBRN practitioner or not seeing any practitioner. If allowable by the IRB, we propose the following options:
 - a. Invite the new dentist into the Network so the patient can continue to be followed by the new practitioner.
 - b. Ask the patient to return to the original practitioner only to collect the end of treatment and one year post-treatment data.
 - c. Ask the patient to visit a different network practitioner who is participating in the study only to collect study related data.
 - d. If the patient is moving, provide a list of network practitioners in the area the patient is moving to.

Other Administrative and Design Methods to Increase Retention Rates

- 1) IRB/Informed Consent Considerations to Reduce Attrition

- a. Incorporate into the informed consent form (ICF) permission for all relevant study personnel, both in the dentist's office as well as the study investigators, and RCs to contact the patient. This will allow communications with the patient by study personnel without having to go through the dental office.
 - b. Incorporate into the ICF permission to see a National Dental PBRN practitioner other than the initial provider for the purpose of data collection. This will expedite data collection in those instances where a National Dental PBRN practitioner retires or sells his/her practice, or where a patient goes to a different non-National Dental PBRN practitioner, or stops seeing a practitioner for routine care.
- 2) Financial, but non-coercive incentive to patients to encourage continuing participation.
- a. Patients will receive \$25 each for the enrollment and end-of treatment visits. For the final study visit, which is approximately after one year of retainer use, they will receive \$50. This amount is purposely larger than the other two, as it is always more difficult to retain patients after active treatment has been completed.

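### Section 5.4.1 lets a patient who later expects to move be terminated, against Appendix D, and permits possibly outcome-related termination after which Section 5.4.2 stops data collection

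*Protocol*

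**What the plan says.** Section 5.4.1 of the protocol introduces two grounds with "An investigator may terminate a study patient's participation in the study if". The first is the patient's best interest. The second is "The patient meets an exclusion criterion (either newly developed or not previously recognized) that precludes further study participation".

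Section 5.2 lists four patient exclusions. Clefts, craniofacial conditions and syndromes are largely fixed before entry, and the 36-month limit refers to the initial treatment plan. The two that can readily arise later are "Patients expecting to move before the completion of the study" and "Patients who have significant physical, mental, or medical conditions that would affect their treatment compliance, cooperation, or outcome".

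For withdrawals not due to an unanticipated problem or safety concern, Section 5.4.2 says that "the date and reason for withdrawal will be recorded, and no additional study data will be collected". Section 6.5 adds a limited recovery: "If withdrawal occurs during an in-office visit, and if the consent was not withdrawn, obtain the applicable study data".

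Appendix D lists a patient's move among the scenarios to be managed. Subject to IRB agreement, it proposes bringing the new dentist into the network, a return to the original practitioner for the end-of-treatment and one-year data, or a visit to another participating practitioner. It adds: "If the patient is moving, provide a list of network practitioners in the area the patient is moving to". It also describes the likelihood of staying in the study as an entry criterion.

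**The concern.** The same event, a patient who comes to expect a move, leads to two different places. Sections 5.2, 5.4.1 and 5.4.2 together permit termination and an end to data. Appendix D sets out how to go on collecting the two assessments on which the primary objectives rest. A site cannot tell which applies.

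The condition criterion raises a different issue, because it is worded by its effect: "conditions that would affect their treatment compliance, cooperation, or outcome". Ending participation on that ground selects on something expected to predict the endpoint. The decision lies with a practitioner who sees how the bite is progressing, and Section 15.4 states that no masking is planned. If such patients leave without an outcome, the observed proportions may be too favorable. An analysis plan cannot recover overbite data that were never collected.

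Little is gained in exchange. Section 2.3 says that the study provides no dental care and anticipates no safety risks, and the first ground in Section 5.4.1 already protects the patient's interest.

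**Working it through.** **1. The sections side by side**

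| Later event | Sections 5.2, 5.4.1, 5.4.2 | Appendix D |
|---|---|---|
| Patient expects to move | May be terminated; then only date and reason recorded | Keep in the study by one of several routes |
| New significant condition affecting compliance, cooperation or outcome | May be terminated; then only date and reason recorded | Not addressed; only the general aim of avoiding bias from incomplete follow-up |

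The conflict is direct for movers. For new conditions there is tension with the aim of Appendix D but no contradiction.

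**2. The plan's own figures (Section 11.2)**

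Inputs: ICC 5%, 3 patients per practitioner, success 70%, stability 50%, attrition 10% and then 20%, 95% confidence (Section 11.3).

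- Design effect: 1 + (3 − 1) × 0.05 = 1.10.
- n = 1.96² × p(1 − p) / 0.05² × 1.10. This gives 422.6 at p = 50% (stated 422) and 355.0 at p = 70% (stated 355). A half-width of 10 points would give only 105.6 at p = 50%, so the stated 10% precision is the full interval width and the half-width is 5 points.
- 422.6 / 0.70 = 603.7 (stated 600). 600 / (0.9 × 0.8) = 833.3 (stated 840).
- Forward: 840 × 0.9 × 0.7 × 0.8 = 423.4 patients for stability, against 422.6 needed. There is almost no reserve beyond the attrition allowances. Each 1% of enrollment is 8.4 patients.

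The sample-size chain reproduces, and no stated figure is in dispute.

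**3. Sensitivity of the two proportions**

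Let p be the true proportion, w the share terminated without an outcome, and q the proportion who would have had the good outcome among those terminated. If they leave the denominator and other losses are unrelated to outcome,

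observed = (p − wq) / (1 − w).

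For success, w is a share of enrolled patients lost before the end-of-treatment assessment. For stability, it is a share of patients already classed as successes who are lost before the one-year assessment. The protocol gives neither w nor q, so both are assumed. Entries are observed minus true, in percentage points.

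| w | Success (p = 70%): q = 0 | q = 35% | q = 70% | q = 100% | Stability (p = 50%): q = 0 | q = 25% | q = 50% | q = 100% |
|---|---|---|---|---|---|---|---|---|
| 1% | +0.71 | +0.35 | 0 | −0.30 | +0.51 | +0.25 | 0 | −0.51 |
| 2% | +1.43 | +0.71 | 0 | −0.61 | +1.02 | +0.51 | 0 | −1.02 |
| 5% | +3.68 | +1.84 | 0 | −1.58 | +2.63 | +1.32 | 0 | −2.63 |
| 10% | +7.78 | +3.89 | 0 | −3.33 | +5.56 | +2.78 | 0 | −5.56 |

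Example: (0.70 − 0.05 × 0.35) / 0.95 = 0.7184, or +1.84 points.

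**4. When the bias reaches the 5-point half-width**

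With q = 0: w = 1 − 0.70/0.75 = 6.7% for success, and w = 1 − 0.50/0.55 = 9.1% for stability. With q at half the overall rate: w = 0.05/0.40 = 12.5% and 0.05/0.30 = 16.7%.

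**The case against.** The strongest reply is that the sections can be read together. Termination is optional, and the criterion must be one that rules out further participation. A mover who can return or be seen elsewhere is arguably not ruled out, so Appendix D would be tried first and termination kept for when it fails. That reading is sensible, but the protocol does not state it, and nothing says which criteria rule out participation or in what order the two provisions apply.

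A reader might infer that eligibility is re-applied throughout the study. The documents do not support that: Appendix A and Section 6.2 place the eligibility assessment at enrollment only. A reader might also infer that ordinary poor compliance is a ground for removal. It is not: the criterion requires a significant condition, and compliance is recorded as study data (Sections 3.2 and 7.1).

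There are safeguards. Section 6.5 recovers data at an in-office withdrawal, but only for that visit; a patient terminated mid-treatment still has no end-of-treatment outcome. Section 15.4 provides practice-level attrition reports and reports on reasons for loss, and Section 5.3.1 pays practitioners per completed visit. These discourage or reveal losses without replacing the missing outcome. How terminated patients enter the proportions may be settled in an analysis plan not shown. That could change the calculation above, but it would not supply the data.

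**Conclusion.** The point holds in two parts. For patients who later expect to move, Sections 5.2, 5.4.1 and 5.4.2 conflict with Appendix D and must be reconciled. The cost is evaluable patients, drawn from attrition allowances that leave almost no reserve. For newly developed significant conditions, termination may be related to outcome and may overstate success.

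A reader might go further and infer that the rule removes likely failures from both primary proportions. The documents do not support that. Nothing in them says that movers do worse, so their loss has no known direction of bias. A would-be failure terminated before the end of treatment would not have entered the stability denominator, which Section 11.3 limits to successfully treated patients. Stability may be overstated only where termination prevents the one-year assessment of patients already classed as successes.

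For 1% to 10% terminated and q between zero and the overall rate, the overstatement runs from 0 to about 8 points for success and 0 to about 6 for stability. It is negative if those terminated would have done better than average. These are ranges over assumed inputs, with terminated patients taken out of the denominator, and are not estimates of what will occur.

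**What to change.** - **Section 5.4.1:** delete the reference to newly developed exclusion criteria and state that the Section 5.2 criteria apply at enrollment only, as Appendix A already schedules. Record a later move or new condition, and follow the patient under Appendix D. Patient request and the best-interest ground remain reasons for withdrawal.
- **Section 5.4.2:** provide that end-of-treatment and one-year overbite data are still collected for patients terminated by the investigator who have not withdrawn consent, where this is in the patient's interest. This matters because Section 5.4.2 is where the data stop, and it also covers patients found after entry to have been ineligible.

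The cost is two short wording changes, IRB review of the amendment (Section 14.2), and a small amount of extra follow-up effort through routes that Appendix D already describes. Treatment is not affected.

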5.4.2 Handling of Withdrawals

In the case of patient withdrawal from the study, staff will only attempt continued follow-up data collection for patients who are withdrawn due to an unanticipated problem or other safety concerns. In these circumstances, only data related to the completion of reporting requirements for the unanticipated problem will be recorded. For patients withdrawn from the study for any other reason, the date and reason for withdrawal will be recorded, and no additional study data will be collected. Patients withdrawn from the study may continue to receive usual dental care as patients of the participating practitioner; however, additional study data will not be collected (except as noted above).

Replacement of patients who withdraw or discontinue early will be allowed, but only during the initial 11 months patient enrollment period. The practitioner may attempt to enroll one replacement patient for each patient enrolled who withdraws or discontinues during the practitioner-specific enrollment period. No practitioner will contribute more than 15 active patients in total to the analyses.

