The cephalometric x-rays and intra-oral frontal photographs obtained as part of routine orthodontic care before treatment and at the time of appliance removal will be used for this research. Practitioners will obtain an additional intra-oral frontal photograph at the time of appliance removal and two other intra-oral frontal photographs at the Final Study Visit (approximately one year after appliance removal/end of active treatment). Practitioners will be asked to de-identify the x-rays and photos and upload them electronically to a central data collection site created and maintained by the CC. De-identification procedures will be detailed in the Practice Training Manual. The RCs will be asked to verify that x-rays and photographs uploaded are de-identified and of good quality. At the end of each data collection period, the SPI or designee will review the x-rays and photographs to measure overbite, mandibular plane angle, and incisor angulation. The related quality management procedures will be specified in the MOP. The measurements obtained will be used to assess the study outcome measures.

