Appendix A: Schedule of Events

Appendix B: Examples of Anterior Openbite

Appendix C: Method to Measure Millimetric Vertical Relapse from Photographs

Appendix D: Patient Retention Plan

APPENDIX A: Schedule of Events

Procedures	Practitioner Screening/ Enrollment	¹ Patient Enrollment/ Baseline (Stage 1 [S1])	^{1,2} Appliance Removal, End of Active AOB Treatment (Stage 2 [S2], Visit 1 [V1]; ~24 months after S1)	Retainer Check Visits (S2, V2-X)	³ Final Study Visit (Stage 3; S2, V1 +10 to 24 months)
Practitioner Recruitment and Enrollment	X				
Obtain Practitioner Characteristics	X				
Informed Consent		X			
Assessment of Eligibility Criteria		X			
Review of Medical/Dental History		X			
Obtain/confirm contact information and preferred method of contact		X	X	X	X
Patient Demographics		X			
Enrollment Visit data collection (Patient and Practitioner)		X			
Cephalometric x-ray		X	X		
Intra-oral frontal photograph		X	X		X
Measurement of the height of right maxillary central incisor			X		X
End of Active Treatment data collection (Patient and Practitioner)			X		
Retainer Use data collection (Patient and Practitioner)				X	
Final Visit data collection (Patient and Practitioner)					X

Foot notes:

1 = Cephalometric x-rays and intra-oral frontal photographs obtained as part of routine orthodontic care before treatment and at the time of appliance removal/end of active AOB treatment will be used.

2 = One additional intra-oral frontal photograph will be obtained at the time of appliance removal/end of active AOB treatment for this research.

3 = Two intra-oral frontal photographs will be obtained approximately one year after end of active treatment for this research.

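### Sections 5.4.2 and 6.5 give opposite data instructions for an in-office withdrawal with consent intact, and 5.4.2 leaves routine end-of-treatment images, hence the success outcome, uncollected

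*Protocol*

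**What the plan says.** Section 5.4.2 of the Protocol splits withdrawals in two. Where the cause is an unanticipated problem or another safety concern, follow-up is attempted but "only data related to the completion of reporting requirements for the unanticipated problem will be recorded". For every other cause, "the date and reason for withdrawal will be recorded, and no additional study data will be collected". The section expects that such patients may remain in usual care with the same practitioner, and repeats that study data collection still stops.

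Section 6.5 describes the withdrawal visit: "If withdrawal occurs during an in-office visit, and if the consent was not withdrawn, obtain the applicable study data", using the forms and steps of the relevant visit. It has two conditions, an office visit and standing consent. It makes no exception by cause of withdrawal.

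Withdrawal with consent intact is a real category. Section 6.5 names it, and section 5.4.1 adds removal by the investigator: "An investigator may terminate a study patient's participation in the study if" a medical situation arises or an exclusion criterion is met.

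On the images, section 3.2 judges success by positive incisor overlap at the end of treatment, from the frontal photograph and the cephalogram. Section 13 describes their source: "The cephalometric x-rays and intra-oral frontal photographs obtained as part of routine orthodontic care before treatment and at the time of appliance removal". Section 5.1 makes permission to use these records a condition of entry, and requires practitioners who routinely take cephalograms before and after treatment. For stability, Appendix A says "Two intra-oral frontal photographs will be obtained approximately one year after end of active treatment for this research".

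**The concern.** There are two separate problems.

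The first is a contradiction. A practice facing a patient who withdraws in the chair, without revoking consent, is told in one section to record two items and in another to complete the visit's data collection. About 210 practitioners are to apply these rules.

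The second is a gap that remains even if the contradiction is settled for the visit itself. A patient may stop taking part during active treatment, stay with the practitioner and finish. The practice will then normally hold the images that classify success, and the patient agreed at entry to the use of such records. No research visit is needed to read them, since section 13 has the study principal investigator or a designee measure the uploaded images. Under 5.4.2 they are never uploaded, so a primary outcome is missing although the information exists. A later analysis plan cannot recover images that sites were told not to send.

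If patients who withdraw differ in success from those who stay, the estimated success proportion is shifted. Replacing withdrawn patients, which 5.4.2 allows during enrolment, restores numbers but does not remove that shift.

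**Working it through.** **The sections side by side**

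- Office visit, consent stands, non-safety cause: 5.4.2 allows date and reason only; 6.5 requires the applicable visit data. Opposite.
- Office visit, consent stands, safety cause: 5.4.2 allows reporting data only; 6.5 has no such limit. Also mismatched.
- Consent revoked: 5.4.2 stops collection and 6.5 does not apply. No conflict.
- Withdrawal outside an office visit: 6.5 asks only for date and reason. No conflict.
- Routine images taken after withdrawal: 5.4.2 bars collection; 6.5 covers only the withdrawal visit. This is the gap.

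**The plan's own figures** (section 11.2: ICC 5%, 3 patients per practitioner; section 11.3: 95% confidence interval)

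- Design effect: 1 + (3 − 1) × 0.05 = 1.10.
- n at a 50% rate: 1.10 × 1.96² × 0.5 × 0.5 / 0.05² = 422.6, against 422 in the table. The stated 10% precision is therefore a total interval width, or ±5 points.
- Before attrition: 422 / 0.70 = 603, against 600.
- With attrition: 600 / 0.9 / 0.8 = 833, or 603 / 0.9 / 0.8 = 837, against 840 (= 210 × 4).

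The target reproduces and already allows for attrition, so this point does not alter it.

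**How many success outcomes are at stake**

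- Planned loss by end of treatment: 0.10 × 840 = 84, leaving 756.
- The share of the 84 who withdraw with consent intact and later have routine images is not given. Assumed range: 10% to 100%.
- Recoverable at most: 0.10 × 84 = 8.4 to 1.00 × 84 = 84.

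**Effect on precision** (70% success, half-width = 1.96 × √(1.10 × 0.7 × 0.3 / n))

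- n = 756: 3.43 points.
- n = 764.4 (10% share): 3.41 points.
- n = 840 (100% share): 3.25 points.

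**Possible bias.** Let a be the fraction of the cohort lost this way (1% to 10%, matching the assumed shares), q their true success rate, and 70% the observed rate. Any other missing patients are taken to resemble those observed. Bias = 0.70 − [(1 − a) × 0.70 + a × q] = a × (0.70 − q).

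- a = 1%, q = 60%: 0.1 point upward.
- a = 10%, q = 30%: 4.0 points upward.
- q = 100%: 0.3 point downward at a = 1%, 3.0 points downward at a = 10%.

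The values of q are assumptions; the documents give none.

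**Outer bounds for all missingness.** With all 84 counted as failures: 0.70 × 756 / 840 = 63.0%. With all counted as successes: (0.70 × 756 + 84) / 840 = 73.0%.

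**The case against.** The best defence is that the sections can be read in sequence: 6.5 governs the withdrawal visit and 5.4.2 what follows. That is a sensible intention, but 5.4.2 does not limit itself to the period after the visit, and this reading leaves the routine images uncollected.

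It is also fair that the direct conflict seldom touches a primary outcome. Appendix A has no study visit between enrolment and appliance removal, so a mid-treatment withdrawal visit has no matching outcome form. The sections differ on success only if withdrawal coincides with appliance removal, and on the one-year measure only if it coincides with the final visit. This stands. The loss of success outcomes comes mainly from the gap in 5.4.2.

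The training manual and coordinator training in section 6 might settle practice across sites; they cannot be checked here. Nor does the permission in section 5.1 say that it survives withdrawal, which is why a consent-form line is needed. For a patient removed because of a previously unrecognised exclusion criterion, recovering the outcome may not improve the estimate.

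A reader might infer more than the documents support:

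- That 5.4.2 bars all further data. It keeps the date, the reason and unanticipated-problem reporting.
- That it discards outcomes already recorded. It stops additional collection and says nothing about deleting or excluding data already held.
- That 63.0% to 73.0% measures this defect. Those bounds cover every cause of loss. Appendix D also lists patients who are lost, who have missing data or who no longer see the enrolling practitioner, and gives separate procedures for them.
- That the success rate will be inflated. No passage links withdrawal to slow or failing treatment.

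**Conclusion.** The point holds in two limited parts. Sections 5.4.2 and 6.5 contradict each other for an in-office withdrawal with consent intact and must be reconciled. In addition, 5.4.2 causes avoidable loss of the success outcome for patients who withdraw from the study but finish treatment in the practice. It does not do the same for stability, because no routine one-year images are planned.

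The size is uncertain. The figure of about 8 to 84 recoverable outcomes is an upper limit at each assumed share, since it supposes that every such patient finishes treatment with usable images. The gain in precision is negligible, at most 3.43 to 3.25 points. The reason to act is possible selection bias, between 0.1 and 4.0 points upward under the assumed success rates of 30% to 60%, and downward if those who withdraw do better than 70%. Neither direction is established. The change is worth making because the loss is avoidable, cannot be repaired in the analysis and is cheap to prevent.

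**What to change.** Amend section 5.4.2 so that it agrees with 6.5 and separates a patient who stops study visits from one who revokes consent.

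- Where consent stands: obtain the applicable data at an in-office withdrawal visit, as 6.5 already provides, and later upload the routine end-of-treatment cephalogram and frontal photograph if the patient finishes treatment in the practice. State how safety withdrawals fit this rule.
- Where consent is revoked: collect nothing further beyond the date, the reason and any required unanticipated-problem reporting.
- Add a line to the consent form confirming that routine images may still be used after study visits stop, unless consent is revoked.

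The cost is one amended paragraph, the consent line with its ethics review, and reminders at sites for a few extra patients. Treatment, visit schedule and sample size do not change.
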